1.2 Drug Profile

Dysport contains a neurotoxin complex that is produced by fermentation of *Clostridium botulinum* bacteria toxin type A, Hall strain. This haemagglutinin complex is composed of a number of proteins naturally produced along with the toxin which is believed to stabilize it but which has no apparent therapeutic effect in its own right. *Dysport* contains nominally 300 U of BoNT-A-haemagglutinin

complex together with 125 µg of human serum albumin (HSA) and 2.5 mg of lactose in a clear glass vial. Further details can be found in the approved leaflet in China.⁴

Dysport is labelled for a dose of 50 U to be injected intramuscularly in five equal aliquots of 10 U each into each of five sites, two in each corrugator muscle and one in the procerus muscle. Retreatment is permitted every three months.⁴

1.3 Risk/Benefit Assessment

In placebo-controlled clinical trials of *Dysport*, very common adverse reactions (> 1/10) following injection were injection site reactions (e.g. erythema, oedema, irritation, rash, pruritus, paraesthesia, pain, discomfort, stinging and haematoma), and headache. Common reactions (> 1/100) included eye disorders (e.g., asthenopia, eyelid ptosis, eyelid oedema, lacrimation increased, dry eye, muscle twitching (twitching of muscles around the eyes), and facial paresis (due to temporary paresis of facial muscles proximal to injection sites, it is predominantly manifested as brow paresis).⁴

Side effects related to spread of toxin distant from the site of administration have been reported, such as dry mouth, excessive muscle weakness, dysphagia, aspiration pneumonia, with fatal outcome in some very rare cases. Hypersensitivity reactions have also been reported post-marketing.⁴

The dose administered and the minimum time between treatments are according to the approved leaflet in China. Steps to reduce complications of ptosis are outlined in Section 6.1.5. Subject will be provided with information on the benefits and risks of their treatment by the physician in accordance with their real clinical practice.

The risks associated with participation in this study are considered acceptable compared to the anticipated high degree of subject and physician satisfaction with treatment and the treatment regimen.

2 CLINICAL STUDY OBJECTIVES

2.1 Clinical Study Objectives

The objectives of this study are to collect subject and physician satisfaction, and long term treatment experience with *Dysport* in the GL in subjects of Chinese origin in a real-life clinical setting.

2.1.1 Primary Efficacy Objectives and Endpoints

The primary objective of the study is to evaluate subject satisfaction after three injection cycles with *Dysport* in the GL.

At Visit 6 (i.e., three weeks, \pm 7 days, after the 3rd injection) subjects will be asked “What is your overall satisfaction after three treatments cycles with *Dysport*?” See [Appendix 1](#), Question 17.

Response options:

- Very Satisfied
- Satisfied
- Dissatisfied
- Very Dissatisfied

The primary endpoint will evaluate the proportion of subjects in each response category.

2.1.2 Secondary Efficacy Objectives and Endpoints

The secondary efficacy objectives and endpoints of the study are:

1. Objective: To evaluate physician satisfaction after three injection cycles with *Dysport* in the GL.

Endpoint: Proportion of subjects in each response category for the physician’s overall satisfaction with *Dysport* after three injection cycles will be evaluated at Visit 6 (i.e., three weeks, \pm 7 days, after the 3rd injection). See [Appendix 2](#), Question 7.

2. Objective: To evaluate subject **CCI** after each injection cycle with *Dysport* in the GL.

Endpoints:

- a. Proportion of subjects in each response category per question answered on the Subject Satisfaction Questionnaire complete at all visits. See [Appendix 1](#)

CCI

Effective

Effective date: 2021-06-28 08:30

CCI

A large black rectangular box covers the majority of the page content, starting below the logo and ending above the page footer. The text 'CCI' is visible in the top-left corner of this redacted area.

Effective date: 2021-06-28 08:30

Effective

2.0

3 OVERALL CLINICAL STUDY DESCRIPTION

This is a prospective, longitudinal, non-interventional, multi-center study to collect subject and physician satisfaction, and treatment experience with *Dysport* in real clinical practice in subjects of Chinese origin.

Approximately 250 subjects are planned to be included in the study to receive three injection cycles with *Dysport* in the GL. The decision by the physician to treat the subject with *Dysport* on a long term basis must be made before including the subject in the study, and has to be clearly separated and independent of the decision to include the subject in the study.

Given the non-interventional nature of the study, subject visits, treatment regimen, and the administration of *Dysport* to treat GL will be carried out according to the physician's real clinical practice and the approved leaflet in China.

The study consists of three injection cycles. Each injection cycle includes an injection visit and a follow up visit three weeks later (\pm 7 days). Following the 1st injection at Visit 1, subsequent injections, i.e., 2nd injection and 3rd injection, will be scheduled three to six months apart. The final follow up visit will be held three to six months after the subject's 3rd injection.

The screening visit and the 1st injection visit may be conducted on the same day. Data will be collected at all visits, if held. Subjects and physicians, independent of each other, will assess the subject's GL severity, and will complete a questionnaire about satisfaction with treatment outcomes at all visits.

Injection practice details for each injection visit, including muscle(s) injected, total dose and volume, dose and volume per injection point, and number of injection points will be collected per the study objectives.

Adverse events (AEs) will be collected during the study.

4 CLINICAL STUDY DURATION AND TERMINATION

The planned clinical study duration is approximately 24 months. The date of end of the clinical study is defined as the date of the last visit of the last subject.

The planned duration of recruitment is approximately six months.

In accordance with the treatment regimen and the physician's real clinical practice, study participation for each subject is anticipated to be approximately nine to 18 months.

The Sponsor may decide to prematurely terminate or suspend the participation of a particular clinical study center (for example, for lack of subject enrollment or non-compliance with clinical study protocol, regulation, or GCP) or prematurely suspend the clinical study (for example, for safety, study drug(s) quality, regulatory, efficacy, or logistical reasons) at any time with appropriate notification.

5 SELECTION AND DISPOSITION OF CLINICAL STUDY POPULATION

5.1 Number of Subjects

Approximately 250 subjects will be included in the study.

To avoid bias in the recruitment of subjects, physician will be asked to include all consecutive subjects during Botulinum toxin A (BoNT-A) consultations to achieve the recruitment target of 20-30 subjects during a restricted and defined period. If consecutive inclusions are not feasible (e.g., administrative constraints), and in order not to disturb the medical activities in the physician's clinic, physician will be authorized to space the inclusions (e.g. inclusion of one subject after every two, or three, etc.), and will follow the same recruitment frequency until achievement of the recruitment target. The modalities for recruitment will have to be determined prior to recruitment start.

5.2 Clinical Study Population Characteristics

In order to be eligible for the clinical study, subjects must fulfill all of the following criteria. These criteria are applicable at screening/baseline.

5.2.1 Inclusion Criteria

1. Adult male or female up to 65 years of age, and of Chinese origin.
2. Moderate (grade 2) or severe (grade 3) glabellar lines at max frown as assessed by the physician **CCI**
3. Prior to and independent of study, subject is seeking long term treatment of their glabellar lines.
4. Prior to and independent of the study participation, physician intended to treat the subject with *Dysport*.
5. Time and ability to complete the study and comply with instructions.
6. Understands the study requirements and signed the informed consent form (ICF).

5.2.2 Exclusion Criteria

1. Hypersensitive to *Dysport* or its excipients.
2. Presence of contraindications to *Dysport* treatment as specified in the approved leaflet in China.
3. Subject is at risk for precautions, warnings, and/or contraindications to *Dysport* as specified in the approved leaflet in China.
4. Subject has an infection in the proposed treatment area.

5. Subjects has had treatment failure experience with other toxins.
6. Pregnant or breast feeding female, or female intending to get pregnant during the study.
7. Participation in a clinical trial, interventional or non-interventional, within 30 days prior to study entry (signature of informed consent).

5.3 Medical History

Relevant history of surgical events and medical conditions shall be documented using medical terminology according to the physician's real clinical practice.

5.4 Previous and Concomitant Medications and Therapies

Previous and concomitant medications and therapies shall be documented using medical terminology according to the physician's real clinical practice.

5.5 Procedures/Reasons for Subject Discontinuation

The importance of completing the entire clinical study should be explained to the subject by the clinical study personnel; however, any subject is free to discontinue participation in this clinical study at any time and for whatever reason, specified or unspecified, and without any prejudice. No constraints are to be imposed on the subject, and when appropriate, a subject may be treated with other conventional therapy.

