6.1.1 Product Description

Table 3 Description and Usage of the Study Drug

	Product
Trade Name	Dysport
Name of Drug Substance	abobotulinumtoxinA
Internal Code	N/A
Pharmaceutical Form	Lyophilised powder
Strength	300 U per vial
Packaging	Single-use vial for reconstitution with 1.5 mL 0.9% Sodium Chloride Injection
Storage conditions	2-8°C
Reconstitution volume	1.5 mL
Dosage	50 U total (0.25 mL total) 10 U per injection site (0.05 mL per injection site)
Route	Intramuscular injection
Dose regimen	Up to three treatment cycles, 3-6 months apart
Location of treated area	Glabellar region

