The recommended dose is 50 U (0.25 mL of reconstituted solution) of *Dysport* divided into five injection sites, 10 U (0.05 mL of reconstituted solution) administered intramuscularly, at right angles to the skin, into each of the five sites: two injections into each *corrugator* muscle and one into the *procerus* muscle near the nasofrontal angle as shown in [Figure 2](#). Intramuscular injections performed with a sterile 29-30 G needle.

Figure 2 Injection Sites for Treating Glabellar Lines

1. Procerus 2. Corrugator 3. Lateral Corrugator/Orbicularis

Immediately after treatment of the patient, any residual *Dysport* which may be present in either vial or syringe should be inactivated with dilute hypochlorite solution (1% available chlorine).

Spillage of *Dysport* should be wiped up with an absorbent cloth soaked in dilute hypochlorite solution.

Any unused product or waste material should be disposed of in accordance with local requirements.

Discard needle and syringe in accordance with local regulations.

6.1.5.1 *Post-treatment Care*

Subjects should be provided with post-treatment care instructions per the physician's real clinical practice.

6.1.5.2 **Treatment Regimen**

The treatment regimen will be performed according to the approved leaflet in China and the physician's real clinical practice. Each enrolled subject will receive treatment with *Dysport* in the GL at Visits 1, 3, and 5, scheduled three to six months apart.

6.2 **Product Packaging and Labeling**

Commercially available *Dysport* will be used in the study.

6.3 **Supplies Management**

6.3.1 **Accountability**

Commercially available *Dysport* will be used in the study. The physician is responsible for supplying the product used in the study, and accountability should be documented according to the physician's real clinical practice.

6.3.2 **Storage of Study Drug(s)**

Dysport should be stored in accordance with the approved leaflet in China.

6.3.3 **Dispensing and Return**

Not applicable; this is a non-interventional study.

6.3.4 **Treatment Compliance Management and Record**

This is a non-interventional study. The decision by the physician to treat the subject with *Dysport* on a long term bases must be made before including the subject in the study. The physician is free to choose *Dysport* modalities of administration in accordance with the approved leaflet in China.

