9.1.2 Injection Visits / Visits 1, 3 and 5 (3-6 months apart)

1. If Screening is performed as a separate visit, confirm subject medical history.
2. Subject to complete self-assessment of glabellar line severity at max frown using the 4-point Categorical Scale. See Section [7.3](#) and [Appendix 3](#).
3. Subject to complete the Subject Satisfaction Questionnaire. See [Appendix 1](#).
4. Physician to complete assessment of the subject's glabellar line severity at rest and max frown using [CCI](#) [REDACTED]
5. Physician to complete the [CCI](#) [REDACTED]. See [Appendix 2](#).
6. Physician or designee to prepare *Dysport* treatment for the subject. See Section [6.1.5](#).
7. Prior to injection, clean the subject's treatment area with a suitable antiseptic solution. See Section [6.1.5](#).
8. The physician will administer *Dysport* treatment. See Section [6.1.5](#).

9. The physician will document injection practice details including muscle(s) injected, total dose and volume, dose and volume per injection point, and number of injection points.
10. Physician or designee will ask the subject about reactions, and document in accordance with the physician's real clinical practice.
11. Schedule the subject's follow up visit three weeks (± 7 days) from the date of injection.

9.1.3 Follow up Visits / Visits 2, 4, and 6 (three weeks (± 7 days) from last injection visit)

1. Subject to complete self-assessment of glabellar line severity at max frown using the Static 4-point Categorical Scale. See [7.3](#) and [Appendix 3](#).
2. Subject to complete the Subject Satisfaction Questionnaire. See [Appendix 1](#).
3. Physician to complete assessment of the subject's glabellar line severity at rest and max frown
CCI [REDACTED]
4. Physician to complete the Physician Satisfaction Questionnaire. See [Appendix 2](#).
5. Physician or designee will ask the subject about reactions, and document in accordance with the physician's real clinical practice.
6. Schedule the subject's next visit three to six months from the date of the injection visit.

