Appendix 1 Subject Satisfaction Questionnaire

Subject #:

Visit #:

Date of questionnaire completion (DD/MM/YYYY):

Please tick the box corresponding to your preferred answer (only one box should be ticked by question unless otherwise specified).

Complete at Visit 1 ONLY

CCI

4. How satisfied have you been with the aesthetic outcome in the injected area after treatment?

[figure not shown]
- Very satisfied
- Satisfied
- Dissatisfied
- Very dissatisfied

5. How satisfied were you with the comfort of the injection?

- Very satisfied
- Satisfied
- Dissatisfied
- Very dissatisfied

Effective

Effective date: 2021-06-28 08:30

Effective date: 2021-06-28 08:30

CCI

Effective**Complete at Visit 6 ONLY****17. What is your overall satisfaction after three treatment cycles with *Dysport*?**

- Very satisfied
- Satisfied
- Dissatisfied
- Very dissatisfied

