**Complete at Visits 6 ONLY****7. What is your overall satisfaction after three treatment cycles with *Dysport*?**

- Very satisfied
- Satisfied
- Dissatisfied
- Very dissatisfied

Effective

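### Overall satisfaction is asked only after a third injection, so the reported percentage describes three-cycle completers and may overstate satisfaction among all treated subjects

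*Protocol*

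**What the plan says.** **When the overall question is asked.** The primary endpoint is one questionnaire item, subject Question 17, on overall satisfaction after three treatment cycles (protocol 2.1.1; SAP 4.1.1). Appendix 1 marks it "Complete at Visit 6 ONLY". The first secondary endpoint is physician Question 7, marked "Complete at Visits 6 ONLY" in Appendix 2. Visit 6 is timed from the third injection.

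**Whether fewer than three cycles is foreseen.** Table 3 in protocol 6.1.1 gives the regimen as "Up to three treatment cycles, 3-6 months apart", and section 5.5 states that "any subject is free to discontinue participation in this clinical study at any time and for whatever reason, specified or unspecified, and without any prejudice". Section 6.1.5.2, in contrast, says "Each enrolled subject will receive treatment with *Dysport* in the GL at Visits 1, 3, and 5".

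**What happens when a subject stops.** Section 5.5 sets no exit visit or exit questionnaire. The schedule (Table 2) and the visit descriptions (9.1) contain no early-termination visit. The only exit step is at Visit 7, which is also timed from the third injection. Section 3 adds: "Data will be collected at all visits, if held". Section 10.1.3 requires a listing of withdrawn subjects with date, reason and last visit.

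**How the endpoint is analysed.** Protocol 10.1.2 puts the primary analysis on the enrolled population, meaning everyone treated at least once. The SAP bases efficacy mainly on the PPS, with the FAS as reference (7.1.1). The PPS requires an evaluable primary endpoint (6.2). Percentages use non-missing data (7.1.2), nothing is imputed (7.2), and each response category gets an exact 95% CI (7.4.1).

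**The concern.** A subject who attends Visit 3 and declines a second injection completes the routine pre-injection forms but is never asked the overall question. Her physician is not asked either, although that answer does not need her presence. Both leave the numerator and the denominator of the two leading endpoints.

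Dysport is not supplied by the sponsor, and re-treatment follows ordinary practice. It is therefore plausible that some subjects who stop are less satisfied than those who return for a third injection. If so, a percentage among Visit 6 respondents is selected towards satisfied subjects. Reported under an all-treated population label, it could be read as applying to everyone who started treatment.

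**Working it through.** The plan has no figure to reproduce: protocol 10.2 and SAP 3.6 say that the sample size of about 250 does not rest on a calculation, and they give no dropout allowance. The check is therefore logical first and numerical second.

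**Who can contribute an answer**

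| Set | Definition | Can early stoppers have the primary outcome? |
|---|---|---|
| Enrolled population (protocol 10.1.2) / FAS (SAP 6.1) | treated at least once | No; counted in the set, but without an answer |
| PPS (SAP 6.2) | evaluable primary endpoint required | No; excluded by definition |
| Denominator used (SAP 7.1.2, 7.2) | non-missing, no imputation | No |

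Whichever set is used, the percentage is taken among Visit 6 respondents.

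**How far the all-treated figure could differ**

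Inputs:
- N = 250 treated. The planned size is from protocol 10.2; that all 250 are treated is an assumption.
- d = share without a Visit 6 answer: 10%, 20% or 30% (assumed).
- Share of respondents who are satisfied (the top two options combined, for illustration): 92% (assumed). The plan reports each category separately, and the same logic applies to each.

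Formulas:
- respondents n = N(1 − d); stoppers m = N − n; satisfied respondents x = 0.92n
- worst case = x/N (no stopper satisfied); best case = (x + m)/N (all stoppers satisfied)
- exact 95% CI = Clopper-Pearson for x out of n

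| d | n | m | x | Reported | Exact 95% CI | Worst case | Best case |
|---|---|---|---|---|---|---|---|
| 10% | 225 | 25 | 207 | 92.0% | 87.7% to 95.2% | 207/250 = 82.8% | 232/250 = 92.8% |
| 20% | 200 | 50 | 184 | 92.0% | 87.3% to 95.4% | 184/250 = 73.6% | 234/250 = 93.6% |
| 30% | 175 | 75 | 161 | 92.0% | 86.9% to 95.6% | 161/250 = 64.4% | 236/250 = 94.4% |

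Between the bounds, the all-treated figure at d = 20% depends on s, the share of stoppers who would be satisfied: (184 + 50s)/250.
- s = 0.5: 209/250 = 83.6%, which is 8.4 points below the reported 92.0%.
- s = 0.8: 224/250 = 89.6%, which is 2.4 points below.

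The exact CI covers sampling error among respondents only. It overlaps the bounds but does not carry the uncertainty from the missing answers.

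**The case against.** The strongest defence is that the objective itself is worded as satisfaction after three injection cycles. Question 17 measures exactly that in the people who had three cycles. A completer target is a legitimate design choice, and this part of the defence stands. A reader might infer that the study fails its own objective, but the documents do not support that. What remains is a mismatch between a completer-only question and a primary population of everyone treated at least once.

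Three other inferences also go too far.

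- **That early stoppers leave no satisfaction data.** Per-visit items are collected and reported (protocol 2.1.2, endpoint 2a). Question 4 in Appendix 1, on aesthetic outcome, is legible and uses the same four options, although the heading that would show its visits is redacted. Reasons for stopping are listed (protocol 10.1.3) and tabulated by site (SAP 7.3.1), injections are documented (9.1.2), and lack of efficacy is a reportable special situation (8.1.5). Still, none of these is the overall rating, and no legible rule uses them for the overall endpoint.
- **That stopping means dissatisfaction.** Nothing in the documents shows this. Cost, relocation or a persisting effect are other possible reasons. The direction of bias is plausible, not proven, and its size is unknown.
- **That analysis can do nothing.** Best- and worst-case bounds and a count of subjects without an answer disclose the gap without new data, although they do not fill it.

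The timing of any exit rating is also a fair objection. Visit 6 falls three weeks after injection, whereas Visits 3 and 5 fall three to six months after the previous one. Protocol 1.1 says the effect lasts about 4-6 months before severity returns to baseline. Pooling the two kinds of rating could lower the percentage through timing alone, so the remedy has to match the three-week point.

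**Conclusion.** The point holds as a cheap improvement to data collection and reporting. The documents establish that the overall item is restricted to Visit 6 for both raters, that no early-exit assessment exists, and that the analysis rules reduce the result to Visit 6 respondents, although the protocol's primary population is all treated subjects.

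The result should be read as satisfaction among three-cycle completers. It may overstate satisfaction among all treated. How much depends on the stopping rate and on what stoppers would have said, and the documents give neither. With 250 treated and 92% of respondents satisfied, the width of the possible range equals the stopping share: 10 points at 10% stopping, 20 at 20% and 30 at 30%. These figures illustrate the exposure; they do not predict the bias.

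**What to change.** 1. Keep Question 17 and physician Question 7 at Visit 6 as the primary and first secondary endpoints, unchanged.
2. Add the overall item for subject and physician at the three-week follow-ups, Visits 2 and 4, worded along the lines of *after the Dysport treatment cycles you have received*. The timing then matches Visit 6.
3. Allow an optional exit rating, at the next scheduled visit or remotely, when a subject will not be re-injected. Protocol 9.1.3 already books that visit: "Schedule the subject's next visit three to six months from the date of the injection visit". Report this rating separately, because the effect may have waned by then.
4. Record the reason for stopping from a structured list that includes dissatisfaction with the result and a persisting effect.
5. In the SAP, beside the primary result, report for all treated subjects the three-week overall satisfaction at the last cycle received, the number with no Visit 6 answer, and best- and worst-case bounds.
6. Reconcile Table 3 with section 6.1.5.2 on the number of cycles, and state how a subject with fewer than three is to be classified.

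Cost: a protocol amendment with ethics committee approval across the 10 planned centres, a short eCRF change and a few SAP tables. No extra visit is normally needed. Some leavers will still not answer, the added item is worded slightly differently from Question 17, and the satisfied percentage may be lower. If data collection is too advanced for an amendment, the count without a Visit 6 answer and the bounds in item 5 need only a SAP change.
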